5.1.3.4 Patient pathway

5.1.4 Study 3: Repeatability of microstructural imaging

5.1.4.1 Primary objective:

To determine the repeatability of microstructural imaging sequences.

5.1.4.2 Method

10 patients who meet the study criteria will be identified from weekly MDT meetings and urology clinics at Royal Free and University College Hospitals. Eligible participants will be contacted in person or by telephone and entered into a screening log kept on a secure NHS computer within the NHS firewall. Patients will be invited to have two MRI scans repeated ≤ 14 d apart. All patients will be provided with a participant information sheet (PIS) and copy of the consent form a minimum of 24 h in advance.

Consent will be obtained for scans at the time of attendance for the MRI scan by the investigator or a designee. They will explain that participants are under no obligation to partake or provide a reason for declining to partake in the study and are able to withdraw at any time. A copy of the signed consent form will be provided to the patient.

MRI will be performed in a 3T MRI scanner at UCL/UCLH and routine clinical safety procedures followed. 3D multi-parametric MRI of the kidney(s) will include the following sequences:

[figure not shown]
- Localisation imaging
- Anatomical T2-weighted imaging
- Diffusion imaging with multiple b-values for VERDICT modelling.
- 3D gradient echo imaging (fat fraction, T2* and quantitative susceptibility mapping)
- Perfusion imaging using dynamic contrast enhanced (DCE) MRI and/or arterial spin labelling (ASL).

Patients will receive an intravenous injection of gadolinium contrast at a dose of 0.1 mmol/kg via an intravenous cannula for DCE-MRI. Gadolinium is standard-of-care for clinical MRI of the kidneys (and many other body parts).

Each patient will have a repeat scan performed with the same protocol ≤ 14 days.

MRI images will be pseudo-anonymised and analysed offline.

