Print Name (in full):[name].....

Position:Research Governance Manager

IDENTIFIERS	
IRAS Number	323984
REC Reference No.	
Sponsor Reference No.	162190
Other research reference number(s) (if applicable)	UCL Data protection: Z6364106/2023/11/12
Full (Scientific) title	A two site pilot study of functional and microstructural imaging using magnetic resonance imaging in patients with renal tumours
Health condition(s) or problem(s) studied	Cancer
Study Type i.e. Cohort etc	Interventional study
Type of trial:	Prospective pilot study
Trial design and methods:	
Patients with known renal tumours will be identified from clinic and MDTs at the Royal Free.
 
Study 1: 20 patients - histological analysis of renal tumours retrieved from the RFH tissue biobank.
 
Study 2: 10 patients – Comparison between MRI and co-registered tumour histology in patients undergoing nephrectomy. Patients undergo a single MRI scan prior to standard of care surgery.
 
Study 3: 10 patients – Repeatability study of microstructural renal MRI. Patients undergo two MRI's within 14 days.

Trial duration per participant:	Single visit (study 2), two visits (study 3)
Key Study milestones	
3 months: ethics and R&D approvals completed
 
4 months: CRF training completed and first patient recruited
 
12 months: Last prospective patient recruited
 
18 months: Data analysis complete

Planned trial sites:	Two sites: Royal Free London Hospital and University College London Hospital
Total number of participants planned:	
20 participants: Study 1.
 
10 participants: Study 2.
 
10 participants: Study 3.

Main inclusion/exclusion criteria:	
Inclusion criteria:
 
 1) Aged 18 and over 2) Confirmed renal tumour ≤ 7 cm planned for surgical resection 3) Willing and able to provide written informed consent 4) Able to lie supine for the duration of an MRI 
Exclusion criteria:
 
 1) Contraindication to MRI e.g., cardiac pacemaker 2) Contraindication to MR contrast agents 3) Pregnancy 4) Breastfeeding 5) Deranged renal function (eGFR <30) in the last three months. 6) Previous treatment of the renal tumour e.g., ablation, radiotherapy
Statistical methodology and analysis:	Prospective pilot study, no specific statistical methodology
FUNDING & OTHER	
Funding	NIHR UCLH BRC: BRC1125/HEI/RH/110410: £48,712
Other support	.
STORAGE of SAMPLES / DATA (if applicable)	

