3. TRIAL DESIGN

The study is a prospective cohort study in which participants will be scanned prior to surgery. Where possible scans will be performed as part of the patient's routine clinical care to minimise the burden on participants in terms of additional hospital visits.

The study duration will be 24 months.

Imaging in this study will take place at University College London Hospital. Patients may be referred from MDTs and urology clinics from The Royal Free Hospital and all surgery and histopathology will be performed at Royal Free Hospital.

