5.1.3.3 Method

10 participants will be identified according to the study criteria and whom are planned for surgery at the Royal Free Hospital will be identified from weekly MDT meetings and urology clinics at Royal Free Hospital. Eligible participants will be contacted in person or by telephone and entered into a screening log kept on a secure NHS OneDrive account. Patients who satisfy the inclusion and exclusion criteria will be invited to have an MRI scan at University College Hospital University College London Hospital prior to their surgery and provided with an invitation letter, participant information sheet (PIS) and copy of the consent form a minimum of 24 h in advance by email or in person.

Consent will be obtained for scans at the time of attendance for the MRI scan by the investigator or a designee. They will explain that participants are under no obligation to partake or provide a reason for declining to partake in the study. A copy of the signed consent form will be provided to the patient.

MRI will be performed in a 3T MRI scanner at UCLH and routine clinical safety procedures followed. 3D multi-parametric MRI of the kidney(s) will include the following sequences:

[figure not shown]
- Localisation imaging
- Anatomical T2-weighted imaging
- Diffusion imaging with multiple b-values for VERDICT modelling.
- 3D gradient echo imaging (fat fraction, T2* and quantitative susceptibility mapping)
- Perfusion imaging using dynamic contrast enhanced (DCE) MRI and/or arterial spin labelling (ASL).

Patients will receive an intravenous injection of gadolinium contrast at a dose of 0.1 mmol/kg via an intravenous cannula for DCE-MRI. This is standard-of-care for clinical MRI of the kidneys (and many other body parts).

MRI images will be pseudo-anonymised and analysed offline. CT scans performed as part of the patients routine clinical care will be obtained from the local PACS (UCLH / RFH), pseudo-anonymised and analysed in conjunction with the MRI scans offline.

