7. DATA MANAGEMENT

7.1 Confidentiality

The study is compliant with the requirements of the General Data Protection Regulation (2016/679) and the UK Data Protection Act (2018). All Investigators and study site staff will comply with the requirements of the General Data Protection Regulation (2016/679) with regards to the collection, storage, processing and disclosure of personal information, and will uphold the Act's core principles. UCL is the data controller; the UCL Data Protection Officer - [contact] The data processors are [name].

Only clinicians involved in the direct care of the patient will have access to personal information. The clinician will enter pseudo-anonymised data on to a database which will only be accessible by researchers in the research team. The 'key' which will have study numbers associated with the patient's hospital number will be stored on secure NHS computers at UCLH, only accessible by clinical fellows and the chief investigator using a password.

Patient consent forms will be held in locked desks at UCLH. Only the Principal Investigator and the nominated Clinical Research Fellow(s) working on the project at RFH / UCLH will have access to this information. Patients on the pseudo-anonymised database will have a study number and relevant clinical information about their renal tumour. This information will include the patient's age, clinical details about renal cancer (location, histopathology results, blood tests). The pseudo-anonymised database will be stored on UCL computers, which will also be password protected. Similarly, all data stored in UCL computers will be anonymised.

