10. ASSESSMENT AND MANAGEMENT OF RISK

We do not anticipate significant risks for the participants associated to the study. The main risks are associated with the additional MRI acquired.

MRI is a safe technique and the scans performed in this study will follow routine clinical procedures and using clinical equipment. Patients will be screened by a trained radiographer to ensure that no risks are introduced e.g., metallic objects being brought into the magnetic field of the scanner. Patients will wear earplugs and headphones during the MRI scan to protect from the loud noises generated.

Patients may receive a gadolinium contrast injection which is routinely used in clinical MRI scans of multiple body sites including the kidneys. It is associated with a very low rate of immediate adverse events (0.06-0.09%) and most adverse events are mild e.g., nausea and vomiting. The incidence of acute, severe allergic reactions is estimated to be 0.0025-0.005%(19). Trained medical personnel will always be present to manage this situation. While the patient is in the MRI scanner regular contact will be made between the research team in the control room and the patient. Patients will hold an emergency call button to raise attention or terminate the scan if required.

The scanner software employs a series of safety checks to ensure that any specific set of scan parameters are safe to use. A local institutional quality control procedure is in place locally and will be used to approve any modifications to the pulse sequence software. Specifically, all code modifications are independently checked by two experienced physicists to ensure that:

- All code modifications are fully documented
- All software safety checks are still carried out
- Code modifications do not affect the validity of these software checks
- A risk assessment is produced for each approved set of code modifications to show that the manufacturer's calculations of physiological effects remain valid.

All RFH, UCLH and UCL individuals involved in this study will have received the adequate health and safety training regarding MRI and tissue handling. Therefore, we do not foresee any potential risk given that all protocols are followed accurately. Well established procedures are in place at RFH, UCLH and UCL to cope with the unlikely event of a breach of health and safety protocols.

11.RECORDING AND REPORTING OF ADVERSE EVENTS

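### Does naming UCL/UCLH as the Study 3 imaging location leave the scan-rescan pairs open to a change of scanner?

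*Protocol*

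**What the plan says.** Four places in the protocol bear on where scanning happens.

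- **Section 5.1.4.2 (Study 3, Method):** "MRI will be performed in a 3T MRI scanner at UCL/UCLH and routine clinical safety procedures followed". The section also requires a second scan within 14 days under the same protocol.
- **Section 5.1.3.3 (Study 2, Method):** "MRI will be performed in a 3T MRI scanner at UCLH and routine clinical safety procedures followed". The sentence is the same apart from the location.
- **Section 3 (Trial Design):** "Imaging in this study will take place at University College London Hospital". This is a statement about the whole study, and it puts surgery and histopathology at the Royal Free.
- **Identifiers table, planned trial sites:** "Two sites: Royal Free London Hospital and University College London Hospital". It does not say which site does the imaging, and UCL is not listed.

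Elsewhere the protocol treats the university and the hospital as separate bodies. In section 7.1 the linkage key "will be stored on secure NHS computers at UCLH", whereas "The pseudo-anonymised database will be stored on UCL computers". Section 10 refers to "All RFH, UCLH and UCL individuals involved in this study".

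**The concern.** The only stated objective of Study 3 (section 5.1.4.1) is repeatability, that is, how far a measurement moves when the same patient is scanned again under unchanged conditions. A change of scanner between the two scans would break that condition. The paired differences would then carry a scanner component, and the result would be closer to reproducibility across equipment. It also feeds a later study, because section 2.2 lists repeatability and the planning and powering of a validation study among the secondary objectives.

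Against that background, it is uncomfortable that the sub-study most sensitive to the scanner has the loosest wording on location. The protocol distinguishes UCL from UCLH elsewhere, so a literal reader can take the slash as two possible locations, one of them not a listed site. The visible text fixes the protocol and the interval for the second scan but does not name the scanner.

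**Working it through.** The protocol states no calculation on this point, so the check is mainly a comparison of text.

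**Step 1. Is there a mismatch?** Yes. Section 3 and section 5.1.3.3 name the hospital, and section 5.1.4.2 adds UCL. The site list adds little, since it names two hospitals and is silent on which one scans.

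**Step 2. Does the slash mean two scanners?** The surrounding text points the other way.

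- Section 3 covers all imaging and makes no exception for Study 3.
- Section 10 says "the scans performed in this study will follow routine clinical procedures and using clinical equipment".
- Section 11.3 has unexpected findings entered on the trust's radiology system, which presupposes a hospital scan.
- Section 15 describes the study as carried out in a hospital.
- Section 5.1.4.2 itself refers to a single scanner and to routine clinical safety procedures.
- Loose naming is common in this document. Section 5.1.3.3 gives the hospital's name twice in two forms, and sections 12.2 and 13 write the two institutions with a slash for joint bodies.

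**Step 3. Would pairs be split?** This needs a further step that no section supports. The second scan is tied to the same protocol, and matching the scanner is ordinary practice for a team measuring repeatability. The Study 3 pathway figure, the patient information sheet and the CRF are not visible, so their silence cannot be assumed.

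**Step 4. What would a split do?** The inputs here are assumptions; only the 10 pairs come from the protocol. Let w be the within-scanner SD, k·w the between-scanner SD, and m the number of pairs that cross. Then

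within-subject variance = w²(1 + (m/10)k²), so the repeatability coefficient is multiplied by √(1 + (m/10)k²).

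| m | k = 0.5 | k = 1.0 |
|---|---|---|
| 0 | 1 | 1 |
| 1 | √1.025 = 1.012 | √1.1 = 1.049 |
| 2 | √1.05 = 1.025 | √1.2 = 1.095 |
| 10 | √1.25 = 1.118 | √2 = 1.414 |

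For scale, the 95% confidence limits for a within-subject SD from 10 pairs are √(10/χ²) times the estimate, or 0.699 to 1.755. Inflation from one or two stray pairs is small beside that. The table runs from no effect to 41% depending on an m and a k that the protocol does nothing to suggest. It describes the assumptions and cannot be read as a measure of any fault in the plan.

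**The case for a change.** The strongest case for acting is that a reader cannot be certain from section 5.1.4.2 alone where Study 3 scans take place, and that other text leaves room for visits to differ. Section 3 has scans done within routine care where possible, and section 4.3 allows for an appointment that already exists, so one scan of a pair might be a routine booking and the other a research booking. Section 4.3 also makes fasting optional. Section 8 speaks of iterative development, and section 10 foresees changes to pulse sequence software. A sentence fixing the scanner and preparation, and a record of sequence version, would cost little.

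The naming mismatch stands. The rest does not amount to a fault in the plan. A routine booking is no evidence of a different scanner. Optional fasting is an instruction that a team would naturally keep the same for both visits, and the unseen documents may already say so. On software, section 10 already requires every code modification to be documented and checked independently by two physicists. These requests would add detail; none corrects a stated rule that gives a wrong result.

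**Conclusion.** The difference in location wording is genuine but clerical. Taken as a whole, the protocol describes hospital imaging at University College London Hospital, and nothing indicates a second scanner or a pair divided between scanners. If both scans of each patient use the same hospital scanner, the effect on the Study 3 repeatability estimate is zero. That conclusion rests on two assumptions: that section 3 governs all sub-studies, as its wording implies, and that the team keeps scanner and preparation constant within a pair, as anyone estimating repeatability would. The objective, the 10 pairs, the interval and the same-protocol requirement are unaffected. Aligning the name is housekeeping for whenever the text is next edited, and no part of the design or analysis depends on it.

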5.1.4.3 Patient pathway

5.2 Material / Samples

Pseudo-anonymised data (MRIs, CTs, digitalised histopathology sections and patient information such as tumour type and grade) will be stored in university (UCL) computers.

The Royal Free Hospital NHS Trust will process, store and dispose of histopathological sections from nephrectomy specimens as part of routine clinical practice in accordance with all applicable legal and regulatory requirements, including the Human Tissue Act 2004 and any amendments thereto.

5.3 Discontinuation/withdrawal of participants

Reasonable travel expenses will be covered and participants given a £10 Amazon voucher as a token of appreciation. Participants may withdraw from the study at any time and without giving a reason without this affecting their clinical care or legal rights.

5.4 Definition of End of Trial

For the prospective dataset collection we will consider the end of the study as the recruitment of the last patient. UCL BRC project funding ends 24 months after the project begins. Linked anonymised

data will be securely stored on University computers for 20 years to enable potential long-term predictions of survival and tumour recurrence.

6. FINANCE AND SUPPLY OF EQUIPMENT

The research costs for the study have been supported by NIHR University College London Hospitals Biomedical Research Centre (BRC1125/HEI/RH/110410). Value: £48,712.

7. DATA MANAGEMENT

7.1 Confidentiality

The study is compliant with the requirements of the General Data Protection Regulation (2016/679) and the UK Data Protection Act (2018). All Investigators and study site staff will comply with the requirements of the General Data Protection Regulation (2016/679) with regards to the collection, storage, processing and disclosure of personal information, and will uphold the Act's core principles. UCL is the data controller; the UCL Data Protection Officer - [contact] The data processors are [name].

Only clinicians involved in the direct care of the patient will have access to personal information. The clinician will enter pseudo-anonymised data on to a database which will only be accessible by researchers in the research team. The 'key' which will have study numbers associated with the patient's hospital number will be stored on secure NHS computers at UCLH, only accessible by clinical fellows and the chief investigator using a password.

Patient consent forms will be held in locked desks at UCLH. Only the Principal Investigator and the nominated Clinical Research Fellow(s) working on the project at RFH / UCLH will have access to this information. Patients on the pseudo-anonymised database will have a study number and relevant clinical information about their renal tumour. This information will include the patient's age, clinical details about renal cancer (location, histopathology results, blood tests). The pseudo-anonymised database will be stored on UCL computers, which will also be password protected. Similarly, all data stored in UCL computers will be anonymised.

7.2 Personal Data breaches

Personal data breaches will be immediately reported to the UCL Information Security Group (ISG) and the UCL Data Protection Officer, and to the Sponsor via the [UCL JRO research incident reporting form](#) (as per form and guidance: <https://www.ucl.ac.uk/legal-services/guidance/reporting-loss-personal-data>). The following information will be provided: full details as to the nature of the breach, an indication as to the volume of material involved, and the sensitivity of the breach (and any timeframes that apply). Sites will additionally follow their Trust incident reporting mechanisms, and will document this within their TMF/ISFs.

8. STATISTICAL CONSIDERATIONS

This study is developing novel imaging techniques at a pilot / proof of concept stage. At this stage there isn't a significant statistical requirement and any statistical analysis required will be performed in house.

As many of the imaging techniques have had limited use in renal imaging there are no data from which to reliably calculate a sample size. However, we will be developing the technology iteratively and will use the findings from this study to inform and power future studies.

9. Planned recruitment rate

We anticipate to be able to recruit two patients per month.

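### Does an anticipated rate of two patients per month contradict the plan to recruit 20 prospective patients by month 12?

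*Protocol*

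**What the plan says.** The forecast in Section 9 of the protocol is one sentence: "We anticipate to be able to recruit two patients per month". It does not say whether the rate applies to the project, to each study or to each site.

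The Key Study milestones in the identifiers table give the calendar. Regulatory steps come first ("3 months: ethics and R&D approvals completed"). The start of enrolment follows ("4 months: CRF training completed and first patient recruited"), then the close of enrolment ("12 months: Last prospective patient recruited"), and the calendar closes with the results ("18 months: Data analysis complete").

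The same table plans 10 participants for Study 2 and 10 for Study 3. The 20 cases of Study 1 come from an existing biobank (Section 5.1.2.2), so they do not draw on the rate.

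Section 5.4 ties the end of the study to recruitment, not to a date: "For the prospective dataset collection we will consider the end of the study as the recruitment of the last patient". On money, that section sets a separate limit: "UCL BRC project funding ends 24 months after the project begins". Section 3 gives the same 24 months as the study duration.

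**The concern.** A reader who multiplies the stated rate by the stated window does not get the stated target. Eight months at two per month falls short of 20, and the protocol mentions no other source of prospective patients. Two things could be at stake. If month 12 closed recruitment, the study would end with fewer patients than planned, which matters when each prospective study has only 10. If recruitment instead ran on, the six months between the last patient and the month-18 analysis milestone would shrink. Work also remains after the last enrolment. In Study 3, "Each patient will have a repeat scan performed with the same protocol" up to 14 days later (Section 5.1.4.2), and in Study 2 the tumour must still be resected, sectioned and stained (Section 5.1.3.3).

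**Working it through.** **Inputs.** Rate 2 per month (Section 9). First patient at month 4, last at month 12, analysis complete at month 18, approvals complete at month 3 (identifiers table). Target 10 + 10 = 20 (identifiers table). Funding to month 24 (Section 5.4). Assumption: one rate covers Studies 2 and 3 together.

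**Patients expected by month 12 (rate × window).**

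| Reading of the window | Calculation | Patients |
|---|---|---|
| Elapsed time, month 4 to 12 | 8 × 2 | 16 |
| First patient at month 4.0, then one every half month | 1 + 8 × 2 | 17 |
| Months 4 to 12 counted inclusively | 9 × 2 | 18 |
| Start at approvals, month 3 (earlier than the stated first patient) | 9 × 2, or 1 + 9 × 2 | 18 to 19 |

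No project-wide reading reproduces 20. The shortfall is 2 to 4 patients on the readings that respect the month-4 start, and 1 to 2 with a month-3 start.

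**When the 20th patient arrives.** From month 4: 4 + 20/2 = 14, or 4 + 19/2 = 13.5 with the first patient at month 4.0. If month 4 counts as a full month: 3 + 20/2 = 13. The slip against month 12 is therefore 1 to 2 months.

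**Rate that month 12 requires.** 20/8 = 2.5; 19/8 = 2.375; on the inclusive count, 20/9 = 2.22. Against a forecast given as a whole number, 2.22 and 2.375 round to two, and 2.5 is the limit of rounding.

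**Chance variation.** Suppose the true mean rate were exactly 2 and arrivals followed a Poisson process (an assumption). The probability of 20 or more by month 12 is then 0.19 with a mean of 16, 0.26 with a mean of 17 and 0.35 with a mean of 18. The milestone is optimistic, but not out of reach.

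**Other scopes of the rate.** At two per month in each study, 10/2 = 5 months fill each one, so both are full by 4 + 5 = month 9 and the mismatch disappears. The text does not state this reading, nor does it exclude it.

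**Time left after the last patient.** To the analysis milestone: 18 − 12 = 6 months as planned, against 18 − 14 = 4 to 18 − 13 = 5 months at the stated rate, less up to 14 days if the last patient is in Study 3. To the end of funding: 24 − 14 = 10 months.

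**The case for a change.** The case for a correction is a reasonable one. Every input is in the protocol, and no project-wide reading gives 20 by month 12. The readings that would remove the conflict are not written down. A per-site rate is poorly supported, because Study 2 recruits only through the Royal Free. A per-study rate is not mentioned. The identifiers table lists 10 and 10 as separate totals, so 20 distinct patients is the plainer reading. A funder or site judging progress would find two different expectations: a project recruiting exactly as Section 9 foresees would still miss its month-12 milestone. Time for surgery, histology and a repeat scan comes out of the shortened interval, and the rate shows no allowance for withdrawals or unusable scans. The remedy would take one line.

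The arithmetic stands, and so does the remark that Section 9 leaves the scope of the rate open. The consequence does not. The loss of patients depends on recruitment closing at month 12, and no section says that it does; Section 5.4 lets the last recruitment define the end. The squeeze on analysis depends on the work needing six months after the last patient, and the protocol does not say so. Section 8 describes iterative development, and Section 18 foresees results being presented throughout the project, so analysis need not wait for the last enrolment. Being cheap to correct is not a reason to amend a protocol when the correction changes nothing that is done or concluded.

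**Conclusion.** The mismatch is real on a project-wide reading but small: about 16 to 18 of 20 patients by month 12, and a last patient about one to two months late. It is a loose planning forecast, not an error in the design. It rests on treating an anticipated, whole-number rate of unstated scope as exact, and it vanishes if the rate is meant per study. Even on the least favourable reading, all 20 patients are recruited by about month 14, with 10 months of funding left and about four months to the analysis milestone. No objective, endpoint, eligibility rule, analysis or safety provision depends on the month-12 line. The study team can manage the slip as recruitment unfolds. Restating the milestone would bring no gain in what the study does or can conclude, so no change is called for. Confidence in the arithmetic is high; confidence that the protocol truly contradicts itself is only moderate, because the scope of the rate is not given.
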